2.1 Population

The study's population is the full universe of schools in the Choma and Livingstone provinces of Zambia (a total of 218 schools). The schools were provided to the authors by the Zambian Ministry of Education. 28 schools were randomly selected for a pre-test RCT (randomly assigning 14 schools to treatment, and 14 schools to control). For this reason, the final number of schools analyzed in this study is 204 (excluding already treated schools from the pilot RCT). The schools are split between primary (grade 1 to 7) and secondary schools (grade 8 to 12). In order to not interfere with exam periods, the Ministry of General Education and GIZ decided to implement the JIC among children in grade 6 in primary schools, and grade 11 in secondary schools. Before the intervention, we contacted all 204 eligible schools. During this process, several schools were found to not exist, to be double-counted or to be a different institution altogether (e.g., kindergartens mislabeled as primary schools). The final set of schools was then 170.

The descriptive statistics of the school sample is given in Table 1. On average, the schools have 80 students¹ and 74 percent of the sample are in Choma. 88 percent of schools are considered rural, i.e., they do not lie in a major town. 4 percent of the sample have received a JIC before. The school's funding is as follows. The vast majority (80 percent) are funded by the Government of the Republic of Zambia (GRZ).

¹We caution that the data behind this variable is highly noisy and based on estimates. For this reason, the data was not used when implementing our block-randomization scheme.

3 percent are funded by the community, 12 percent are privately funded and 5 percent are funded through non-standard grants. Schools' access to governmental and health facilities is captured by three variables. First is the distance to the nearest District Board of Education (DEBS, average of 36 kilometers). Second is the distance to the nearest so-called youth-friendly corner (YFC, average of 20km). Third is the distance to the nearest health facility (HF, average of 4km).

Table 1: Descriptive Statistics of Schools

		N	Mean	SD
School characteristics				
	Students	169	79.0	58.4
	Choma	170	73.5	44.2
	Primary	170	88.2	32.3
	Rural	170	60.0	49.1
	JIC before	170	3.5	18.5
Funding				
	GRZ	157	80.3	39.9
	Community	157	3.2	17.6
	Private	157	12.1	32.7
	Grant	157	4.5	20.7
Location				
	Lat	160	-16.8	2.8
	Lon	160	26.6	0.6
Facilities				

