3.1 Baseline

The baseline data collection, conducted by a team of 10 trained enumerators divided into 3 groups, lasted about two months from March 16, 2017 to April 11, 2017 and from May 24, 2017 to July 11, 2017 for a total of 52 days. Data collection had to be interrupted during the month of April due to a month-long school break. The survey instrument is attached to this document. The prime reason for the baseline survey—in addition to collecting outcomes before the intervention takes place—was to map the entire friendship network in a given grade (more below).

Once data collection started, the survey team found additional ineligible schools that were either unreachable by car, did not have the targeted grades or were closed. Overall, the survey team managed to conduct a baseline in 98 out of the 102 schools in the treatment group (96% of the target), 28 out of 34 schools in the control 1 category, and 7 out of 34 in control 2. The final sample, thus, consists of 133 schools for the baseline survey. 37 of the schools are in Livingstone and 96 schools in Choma. 19 schools are secondary schools and 114 are primary schools. All students in either grade 6 (if primary school) or grade 11 (if lower secondary school) present on the day of baseline were interviewed for a total of 8,276 students.

Since some instruments are sensitive in nature (more below), we opted to administer self-administered surveys on tablet computers supported by ACASI (audio-assisted computerized assisted self-interview software) technology. Specifically, the survey was loaded unto the tablets and each question was accompanied by an audio file that read out loud the question in the desired language (options were Tonga and English). Students were given headphones for increased privacy. After hearing the question, students were to tap on the relevant answer. Finding the correct answer was facilitated by a) maximizing the number of questions with a vignette or picture or color coded, and by

b) positioning the answers on the left, middle, or right panel of the tablet and have the audio file explain where to find the answer. Two enumerators were present to help and assist in case of confusion or any other problem.

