3.2 Network mapping

The network mapping was done as follows. First, enumerators collected attendance lists at every school for the assigned grade. Second, enumerators administered the survey, which included the following question: "Now, I want to know who are the friends that you spend time with in your grade. I am going to read you the names of all students in your grade. For every name, I want you tell me if the student is a friend of yours that you spend time with." Enumerators then recorded each friend of a given respondent on a separate list.

In a third step, the list was then passed on to the principal investigator (PI). In treatment group 1, a random subset of students was chosen for treatment. In treatment group 2, the PI used the R package *keyplayer* (An [and](#) Liu, [2016](#)), to identify the students with the highest in-degree centrality D_i , defined as the sum of incoming friendship nominations from the rest of the network. Specifically, $D_i = \sum_j w_{ji}$, where w_{ji} indicates friendship nominations from j to i . In treatment group 3, the PI used the same package to identify students with the highest edge betweenness centrality. It is defined as:

$$B^i = \sum_k g_{jk}^i, \text{ where } g_{jk}^i \text{ is the number of shortest paths between students } j \text{ and } k, \text{ and}$$

g_{jk}^i gives the amount of those paths running through student i . In other words, key-player selects the group of students who, combined as a pair, are directly connected to the highest number of different students compared to any other combination. The code underlying this procedure, including all realized assignments, is available upon request.

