4.1 Overall effect

H1: We hypothesize that the JIC improves the main and sub-index scores for students in treated schools.

Separately for each targeting strategy, we estimate the overall effect of the JIC by comparing all students in treated schools to all students in control schools,

$$Y_{ij} = \beta_0 + \beta_1 T_j + \beta_2' X_{ij} + \epsilon_{ij}$$

where Y_{ij} represents the respective index for individual i in school j ; X_{ij} marks a vector of salient predictive school- and individual-level pre-treatment covariates³.

T_j is a dummy variable denoting whether a given school was treated or not. To ease interpretation and in line with [Freedman \(2008\)](#), we will use ordinary least squares. For selected robustness tests, we will also include school-random effects. Given that randomization is at the level of the school, we will cluster standard errors at the school level. Moreover, given that we pre-specify one main hypothesis, we will not adjust uncertainty levels for multiple comparisons.

In addition, we pre-register the following additional exploratory hypotheses:

- The JIC improves the knowledge index more strongly than the self-reported behavior index.

³Specifically, at the school-level we include: Students, Choma, Primary, Rural, JIC before, GRZ, Private, Nearest DEBS, Nearest YFC, Nearest HF. At the individual-level, we include age (A1), gender (A2), grade (A3), religion (A4), father's primary job (A5), father's literacy (A6 and A7), parents' marital status (A8) and mother tongue (A9).

- 1• The JIC improves the main index more strongly in urban areas as compared to rural areas.

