6.2 Survey instrument

Section X. Logistics and Network Measurement

Questions to be asked and/or filled in by enumerator.

X1	Fill in the name of the school	Name of school _____
X2	Fill in the ID of the school	School ID _____
X3	Ask student: What is your first name? Confirm with student that name was spelled correctly	Student first name _____
X4	Ask student: What is your last name? Confirm with student that name was spelled correctly	Student last name _____
X5	Enter ID of student from enrollment roster	Student ID _____
X6 (baseli ne AND endlin e!)	
Ask student: Now, I want to know who are the friends that you spend time with in your grade. I am going to read you the names of all students in your grade. For every name, I want you tell me if the student is a friend of yours that you spend time with.
 
[Prompt: Slowly read through enrollment list and prompt for answer at every name (pause, look, "is this a friend that you spend time with?"). Whenever student labels individual friend, put down number on the right.]
 
Protocol for AIR: At every school, obtain enrollment protocol from school officials. The protocol needs to be numbered such that every student has a unique ID. Each enumerator then gets one sheet. This requires making copies (by hand or electronically). AIR should write up a protocol on how this is undertaken.
	ID 1 _____ ID 2 _____ ID 3 _____ ID 4 _____ ID 5 _____ ID 6 _____ ID 7 _____ ID 8 _____ ID 9 _____ ID 10 _____ ID 11 _____ ID 12 _____ ID 13 _____ ID 14 _____

Section A. Demographic Characteristics

First, we have some general questions about your background.

A1	What day, month and year were you born?	Day	Month	Year
A2	What is your gender?	Male		
A3	What grade are you in?	Number	_____	
A4	What is your religion?	Islam		
		Catholic		
		Apostolic		
		Pentecostal		

		Anglican Christian, other Other Don't know
A5	What is your father's primary job?	Farmer ...
A6	Does your father have a hard time reading (e.g., a newspaper or a letter)?	Yes No
A7	Can your father write in English?	Yes No
A8	Are your parents married to each other?	Yes No
A9	What is your native language?	Nyanja Lozi Tonga Kaonde English Luvale Lunda Other Don't know

Section B: Knowledge about sexual and reproductive health				
Section B1: Family planning / contraceptives				
Now, we have some questions about contraception. By that we mean ways in which one can avoid getting pregnant.				
B1-1	Have you heard of family planning before?	Yes No		

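### The models adjust for a school-size estimate that the SAP itself distrusts, although a list of the surveyed grade is taken at baseline; this matters mainly for the total, spillover and direct effects

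*SAP*

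**What the plan says.** SAP section 4.1, footnote 3, lists the school-level covariates as "Students, Choma, Primary, Rural, JIC before, GRZ, Private, Nearest DEBS, Nearest YFC, Nearest HF". Equation (1) uses them. Equation (2) and the direct-effect equation carry the same covariate vector, and the total and spillover models are built on equation (1).

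Footnote 1 in section 2.1, attached to the average number of students, warns that the figures are very noisy and rest on estimates. It continues: "For this reason, the data was not used when implementing our block-randomization scheme". The blocking code in section 6.1 accordingly uses four variables, none of them size.

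Section 3.2 reports a second source of size: "First, enumerators collected attendance lists at every school for the assigned grade". The survey instrument (section 6.2, item X6) instructs the survey team: "At every school, obtain enrollment protocol from school officials", and adds: "The protocol needs to be numbered such that every student has a unique ID". Section 3.1 states: "The final sample, thus, consists of 133 schools for the baseline survey". Nowhere does the SAP say that this list will replace Students as the size covariate, or why the estimate is kept.

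Section 1 sets the number treated: at least 30 students per school, and 20% of the grade in larger schools.

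**The concern.** A variable judged too poor for blocking reappears as an adjustment covariate, while a direct count of the surveyed grade is within reach. In the comparison of whole schools this can cost only precision.

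The section 4.3 models differ because they select students within schools. Under the 30-or-20% rule a small grade is mostly or wholly treated and a large grade is one-fifth treated. Once students are pooled across schools, targeted students therefore come disproportionately from small grades and non-targeted students from large ones. In these regressions the size covariate is the term that directly corrects this. If it is measured with error, the correction is incomplete.

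**Working it through.** **1. Plan's own figures.** Table 2 gives Students means of 66, 94, 78, 71 and 86 and SDs of 50, 55, 53, 52 and 76, with 34 schools per arm. The overall mean is 395/5 = 79.0. The within-arm sum of squares is 33 × (50² + 55² + 53² + 52² + 76²) = 554,862 and the between-arm sum is 17,272, so the SD is √(572,134/169) = 58.2 (58.4 with divisor 168). Table 1 states 79.0 and 58.4, so the tables agree.

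**2. Overall effects: precision only.** Let R² be the share of between-school outcome variance explained by true grade size, and λ the reliability of Students. The standard error with Students, relative to that with true size, is √((1 − λR²)/(1 − R²)). Both inputs are assumed.

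| R² | λ = 0.7 | λ = 0.3 |
|---|---|---|
| 0.05 | 1.008 | 1.018 |
| 0.10 | 1.017 | 1.038 |

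A simulation of school means (4,000 runs per setting, true effect 0.20) gave mean estimates of 0.198 to 0.203 whatever the reliability, so no bias appears here.

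**3. How size drives treated status.** Read the rule as treating max(30, 0.2n) of a grade of n, and everyone when n is 30 or less. The 20% part takes over at n = 30/0.2 = 150. The treated share is 30/40 = 75% at n = 40, 30/79 = 38% at the Table 1 mean, and 20% from 150 upward.

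**4. Mean grade size per student in the pooled samples.** Assume grade size follows a gamma distribution with mean 79 and SD 58.4, taking Students as a grade-level figure.
- All students in control schools: 79 + 58.4²/79 = 122.
- Targeted students (weight max(30, 0.2n)): about 91, by numerical averaging.
- Non-targeted students in treated schools: about 140.

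A lognormal distribution gives about 122, 90 and 142.

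**5. Confounding with no size term.** Assume one SD of size (58.4) shifts the index by 0.10, linearly.
- Total effect, random arm: (91 − 122)/58.4 × 0.10 = −0.053.
- Spillover: (140 − 122)/58.4 × 0.10 = +0.031.
- Direct: (91 − 140)/58.4 × 0.10 = −0.084.

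**6. What remains after adjusting for Students.** With classical error and no other covariates, the fraction left is σe²/(σw² + σe²). Here σe² = 58.4² × (1 − λ)/λ, which is 1,462 at λ = 0.7 and 7,958 at λ = 0.3. The variance of size per student within groups, σw², is 43.2 × 122.2 ≈ 5,270 in controls under the gamma and about 5,000 when groups are pooled. The fractions are 1,462/6,462 = 0.23 and 7,958/12,958 = 0.61.

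| Estimand | No size term | Left at λ = 0.7 | Left at λ = 0.3 |
|---|---|---|---|
| Total (random arm) | −0.053 | −0.012 | −0.033 |
| Spillover | +0.031 | +0.007 | +0.019 |
| Direct | −0.084 | −0.019 | −0.052 |

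The lognormal gives slightly smaller residuals. Across both distributions the ranges are about −0.01 to −0.03, +0.01 to +0.02, and −0.015 to −0.05. Adjusting for true size leaves zero in this linear set-up.

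**The case against.** Blocking and adjustment are different decisions. A regression gives a noisy covariate little weight, whereas in Mahalanobis matching the noise would drive the blocks. So footnotes 1 and 3 do not strictly contradict each other, and for the overall effect the complaint is only about precision. That stands. It is also true that R² should be read as what size explains beyond Primary, Rural, Choma, funding and distances, and that the SAP gives neither R² nor λ.

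The SAP also commits, in section 4.4, to rerun everything without covariates. For the overall effect this shows how much the covariates matter. For the section 4.3 samples it removes the size term altogether and gives the larger figures in the no-size-term column, so it is no safeguard there.

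Several stronger readings are tempting but unsupported:
- *The two size measures visibly disagree.* Arm means weighted by surveyed schools give 77.9 students per school, against 8,276/133 = 62.2 interviewed. But those interviewed were the students "present on the day of baseline were interviewed for a total of 8,276 students", so absence alone could produce the gap. A uniform shortfall would also say nothing about reliability. The evidence for noise is footnote 1.
- *The list is an exact count.* Section 3.2 speaks of attendance lists and section 6.2 of enrolment. The latter is an instruction, not a report of what is held.
- *A degree of freedom is wasted.* The replacement uses the same one.
- *The overall effects are biased.* They are not: Students is pre-treatment and schools were randomised.

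**Conclusion.** The point holds as a modest, inexpensive improvement. For equations (1) and (2) there is no bias and a loss of roughly 1-4% of the school-level standard error, under assumed R² of 0.05-0.10 and reliability of 0.3-0.7.

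For the total, spillover and direct models, residual confounding of about 0.01-0.05 index units is possible. This rests on an assumed shift of 0.10 per SD of size and scales with it. If size does not predict the outcome it is zero, and correlated covariates may absorb part of it. The total and spillover figures are for control groups that contribute all their students. Footnote 4 fixes this for the random arm's total effect; I assume it for spillover. For the two centrality arms, a control selection that applies the same rule school by school would largely match the size mix, but footnote 4 does not say how its corresponding share is set. The unadjusted comparisons between strategies in section 4.3 use no covariates and are untouched.

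**What to change.** In footnote 3, replace Students with the number of students on the numbered baseline enrolment list of the assigned grade, as described in section 6.2, and not the number present on the survey day. State its scale now (raw or log). Report the count by arm beside the estimate in Table 2. Keep the old Students estimate only as a sensitivity check.

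The cost is one line in the SAP and a merge of lists that the network mapping already required. There are two small downsides. The list was taken after schools were assigned, though before the intervention. It also exists only for the 133 baseline schools, not for the other 170 − 133 = 37 that were randomised.

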3.3 Outcome measurement

The questionnaire, administered during the base- and endline of the project, includes four substantive sections. The first section (A) administers demographic questions (e.g., gender, religion, etc.). The second section (B) administers questions pertaining to knowledge about sexual and reproductive health. This includes family planning (B1), condoms (B2), HIV/Aids (B3), other STIs (B4). The third section (C) administers questions about self-reported behavior. This includes sex (C1), HIV testing (C2), and access of youth-friendly corners (C3). The final section, only asked during the endline, includes questions about the JIC.

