3.4 Endline

Endline data collection will happen approximately six months after the JIC implementation and will administer the same questions to the same grades identified at baseline. At this point, the endline is scheduled to take place in October 2017.

14 Empirical Analysis

Our primary outcomes of interest are knowledge and self-reported behavior. To assess the degree to which the JIC improved both outcomes, we will create an overall index that standardizes all our outcome variables. This includes all questions in sections B1, B2, B3, and B4. In section C, this includes all questions, but question C1-8. In a second step, we will split the overall index into a self-reported behavior (section A and B), and a knowledge index (section C). In a third step, we will split the index further into the following topics: family planning knowledge (B1), condom knowledge (B2), HIV/Aids knowledge (B3), STIs knowledge (B4), sex behavior (C1), self-reported testing behavior (C2), and self-reported health access behavior (C3). To account for the networked nature

of the trial, we estimate the overall effects, total effects, spillover effects, and direct effects of the JIC on our main index and on our sub-indexes, separately for the three targeting strategies and across targeting strategies.

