We compare the effectiveness of targeting strategies on the total, spillover, and direct effect at the school level by estimating models analogous to equation (2) without covariate controls on the appropriately restricted samples. We note that since the subsamples of treated (or untreated) individuals in the three targeting arms are not comparable, un-adjusted comparisons warrant a causal interpretation only at the group level, and require covariate control (analogous to equation 2) to be interpreted as averages of individual effects.

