4.4 Robustness

To ensure that our estimates are robust, we commit to the following additional checks. Specifically, we will re-run the above analyses

1. Excluding all covariates

2. Using randomization inference

15 Final remarks

We commit to:

- 1• Make all data and code available after the initial publication of any academic paper or 2 years after the experiment is finished, whichever comes first.
- 2• Answer any questions pertaining to our analysis or to this document.
- 3• Make any deviations from this PAP explicit in the paper.

16 Supplementary Information

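### The fixed covariate list leaves out the baseline value of the outcome index, although the outcome questions were asked before treatment in 133 schools

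*SAP*

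**What the plan says.** Section 4.1 describes X_ij as predictive covariates measured before treatment, and footnote 3 then names them. At school level they are Students, Choma, Primary, Rural, JIC before, GRZ, Private and the distances to the nearest DEBS, YFC and HF. At student level: "At the individual-level, we include age (A1), gender (A2), grade (A3), religion (A4", continuing through A9. Nothing from questionnaire sections B or C, which supply the outcome index, is on the list. X_ij enters equations (1) and (2), and the total, spillover and direct-effect models of section 4.3.

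The baseline outcomes exist. Section 3.1 gives the main reason for the baseline survey as mapping friendships, "in addition to collecting outcomes before the intervention takes place". Section 3.3 states: "The questionnaire, administered during the base- and endline of the project, includes four substantive sections". Section 3.4 says that endline "will administer the same questions to the same grades identified at baseline". The instrument in section 6.2 records names (X3, X4) and a roster ID (X5).

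Section 4.3 specifies the comparison of strategies on the network effects "without covariate controls on the appropriately restricted samples", and adds that such comparisons "require covariate control (analogous to equation 2) to be interpreted as averages of individual effects". Section 4.4 lists two checks, "Excluding all covariates" and randomization inference. Neither brings in a baseline outcome, and the plan contains no change score or ANCOVA.

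**The concern.** The plan sets out to adjust for predictive pre-treatment variables but omits the same outcome measured earlier, which is usually among the strongest predictors available. The loss falls on comparisons of roughly 33 schools with 35.

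Only 35 of the 68 randomized control schools were surveyed at baseline, 7 of them from the 34 in Control 2. Adjusting for the baseline index would remove any measured baseline difference among the surveyed schools. It could not repair selection caused by the schools that were not surveyed.

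In section 4.3 the covariates are also meant to support an interpretation, because the subsamples being compared are not alike. The list offered for that purpose contains no prior outcome.

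Missing covariate values are a secondary matter. If software defaults to complete cases, the adjusted analysis uses fewer schools than the no-covariate re-run in section 4.4. That check would then change the sample as well as the model.

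**Working it through.** **Counts in the plan (section 3.1).** These agree with each other: by arm 98 + 28 + 7 = 133; by district 37 + 96 = 133; by school type 19 + 114 = 133. Students per school: 8,276 / 133 = 62.2. Schools per strategy, assuming an even split of the treated: 98 / 3 = 32.7. Controls: 28 + 7 = 35. The SAP gives no power figure to reproduce.

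**Precision (illustrative).** With total SD = 1:

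SE = sqrt{ [ICC(1 − RbX)(1 − pb) + (1 − ICC)(1 − RwX)(1 − pw)/62.2] × (1/32.7 + 1/35) }

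RbX and RwX are the shares of between-school and within-school variance that the listed covariates explain, assumed to be 0.50 and 0.05. pb and pw are the shares of what remains that the baseline index explains. The detectable effect is 2.8 × SE (two-sided 5%, 80% power, also assumed). The last factor is 0.0592.

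At ICC 0.10:

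| Model | Bracket | SE | Detectable effect (SD) | Change in SE |
|---|---|---|---|---|
| Footnote 3 covariates only | 0.0500 + 0.0137 | 0.0614 | 0.172 | – |
| Plus baseline index, pb 0.10, pw 0.09 | 0.0450 + 0.0125 | 0.0583 | 0.163 | −5.0% |
| Plus baseline index, pb 0.36, pw 0.16 | 0.0320 + 0.0115 | 0.0508 | 0.142 | −17.3% |

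The equivalent increase in schools is (0.0614/0.0583)² = 1.11 to (0.0614/0.0508)² = 1.46.

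Sensitivity:

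- ICC 0.05 gives −4.9% to −15.5%; ICC 0.20 gives −5.1% to −18.7%.
- School mean alone (pw = 0) at ICC 0.10 gives −4.0% to −15.3%.
- If the index explains a share r² of the remaining variance at both levels, the SE is multiplied by sqrt(1 − r²): 0.954 for r = 0.3, 0.714 for r = 0.7.
- With only 2% explained at both levels, the SE falls by 1.0%.

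These figures concern school-level comparisons and do not describe the within-school direct effect.

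**Missing covariates.** Table 1 gives N = 157 for GRZ and Private, 160 for nearest YFC and HF, and 169 for Students and nearest DEBS, out of 170.

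- *Funding data by arm.* I enumerated the whole-number counts that fit the rounded percentages in Table 2 and the totals in Table 1. There is one solution: 32 random, 34 indegree, 30 betweenness, 31 Control 1 and 30 Control 2 (sum 157). With 34 schools per arm, the treated schools without funding data number 2 + 0 + 4 = 6.
- *Minimum loss.* The baseline reached "98 out of the 102 schools in the treatment group", so 102 − 98 = 4 treated schools were unsurveyed. At least 6 − 4 = 2 surveyed treated schools would drop out of a complete-case model, or 2 × 62.2 ≈ 124 students. If both are in one strategy, the SE rises by the factor sqrt[(1/30.7 + 1/35)/(1/32.7 + 1/35)] = 1.017.
- *Maximum loss.* 13 + 10 + 1 + 1 = 25 of 133 (19%). This takes the YFC and HF gaps to be the same 10 schools, with no other overlap and every gap in a surveyed school.

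**The case against.** The plan is valid without this change. A randomized school comparison with clustered standard errors, prespecified covariates, a no-covariate re-run and randomization inference needs no baseline outcome, and the SAP nowhere promises one. That is correct: this is an efficiency point.

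The size is assumed throughout, and the percentage gain largely returns the values chosen for pb and pw. That also stands. Five per cent is not a floor, and the absolute figures are fragile. If the listed covariates explained nothing, the starting detectable effect at ICC 0.10 would be 0.231 SD rather than 0.172. If school sizes vary as Table 1 suggests (mean 79.0, SD 58.4, data that the SAP itself calls noisy), the starting SE is about 0.073 and the detectable effect about 0.21 SD. The relative gain hardly moves, so it is the figure to carry forward.

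On imbalance, no baseline outcome difference is displayed, Table 2 shows close balance on the blocking variables, and footnote 2 already provides for excluding the dropped-school problem in Control 2 in robustness tests. The argument is therefore for protection against a possible difference, not for correcting a demonstrated one. Likewise, nothing here shows that a baseline index would make students chosen by centrality comparable with students chosen at random.

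Linkage is uncertain, since section 3.4 promises the same grades rather than the same students. The school mean needs no linkage and keeps most of the gain. The missing-data point presumes complete-case fitting, which the SAP does not state, and its demonstrated minimum is small. None of this removes the omission or argues against the remedy.

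**Conclusion.** The concern holds. The covariate list is closed, the baseline outcomes were collected, and no analysis uses them. The consequence is lost precision in the adjusted school-level models, not bias in equations (1) and (2). Under the stated assumptions the loss is 5-17% of the standard error at ICC 0.10, and 5-19% over ICC 0.05-0.20. It would be near zero if the baseline index predicted almost nothing beyond the listed covariates.

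The missing-covariate gap is real but secondary. Complete-case fitting would lose at least 2 and at most 25 of the 133 surveyed schools. Unequal loss by arm among surveyed schools is not shown. The change should be made, but the trial does not depend on it.

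**What to change.** - In footnote 3, add the baseline value of the same index or sub-index to X_ij for equations (1) and (2) and for the covariate-adjusted models of section 4.3.
- Where students can be linked by roster ID and name, use the student's baseline score plus the school baseline mean, with a missing indicator for students absent at baseline. If linkage fails, use the school baseline mean alone.
- Leave the section 4.3 comparisons that are specified without covariates as they are.
- State a rule for missing covariates, for example mean fill plus a missing indicator, so that the adjusted analysis and the no-covariate re-run use the same schools.

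The cost is SAP wording, since the baseline data are already in hand, plus a check that roster numbers or names match between rounds if student scores are used. The wording should be settled before endline data are seen, because adding the index later would be a discretionary departure from the plan.
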